If there are circumstances such that a participant prefers remote consenting, we will offer a remote consenting visit as part of the screening visit. The patient will be (e)mailed a copy of the consent form prior to the visit. A study physician or NP will schedule a telephone call or video conference call to obtain informed consent, medical history, medication list, and drinking assessment. The consent will be obtained using RedCap e-consent. After consent, the patient will be allowed the option to obtain fasting labs at a local Quest site. Then, remainder of screening procedures, including bloodwork if not done previously, physical examination by study doctor, and procedures described below, will be done at MGH on a subsequent day.

Screen Visit (to determine eligibility)

1. Informed consent
2. Detailed H&P and medications (past and current), Lifetime Drinking History assessment
3. Fasting blood: AST, ALT, GGT, creatinine, albumin, total bilirubin, direct bilirubin, alkaline phosphatase, PT/INR and PTT, CBC, glucose, HbA1c, Hepatitis B sAg, Hepatitis C antibody, PSA (male subjects).
4. ^1H -MRS/MRI of abdomen for quantification of liver fat and to exclude abnormal liver lesions. This scan will also be used to assess VAT for those eligible subjects participating in the baseline visit.
5. Height and weight
6. Liver ultrasound ("Sonosite") may be performed if subjects do not have a diagnosis NAFLD or have had significant changes in health since NAFLD diagnosis. This is an optional procedure intended to provide an easier alternative to MRI for determining if a study candidate has fatty liver. Subjects may opt to have this test, and then could forego MRI and/or blood sampling if they do not have fatty liver.

Baseline Visit

The following procedures will be performed. Depending on availability of appointments for the various procedures as well as subject availability, subjects may be asked to come on 2-3 different days in order to complete all procedures. (For example, the liver biopsy will usually be performed on a different day than other procedures.)

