1. H&P
2. Fasting labs: IGF-I, glucose, AST, ALT, GGT, total bilirubin, direct bilirubin, alkaline phosphatase, albumin, lipid panel, CBC, PT/INR, HbA1c, frozen serum for adiponectin, IL-6, CRP, CK18, and other relevant inflammatory biomarkers, as guided by the histological results
3. Height, metabolic weight, anthropometrics
4. Whole body DXA scan for regional fat
5. 24-hour Food Recall and Modifiable Activity Questionnaire by CRC bionutrition
6. Transient elastography (FibroScan)
7. Liver biopsy. Biopsy will not be done if performed in the 12 months prior to baseline and, in the interval since biopsy, no new treatment initiated and no weight change $>10\%$
8. Stable isotopes for assessment of hepatic de novo lipogenesis
9. Coronary CT angiography (CCTA) performed in individuals who meet the following criteria: BMI $<40\text{kg}/\text{m}^2$, age $\geq 40\text{y}$ for Males or $\geq 50\text{y}$ for Females. Individuals with any of the criteria detailed in "Exclusion Criteria (#22)" above will not undergo CCTA.
10. Peripheral blood mononuclear cells (PBMCs) will be processed for flow cytometry of immune cells and related immune studies at baseline and 12 months, as well as processed and stored for DNA at baseline.

Start of Study Drug

At the conclusion of the baseline visit, subjects will be instructed in reconstituting and administering tesamorelin or identical placebo, and they will self-administer their first injection at the conclusion of the visit. After administration, they will be observed for 30 minutes to ensure no allergic reaction.

Safety Visits (0.5, 1, 2, 3, 6, 9, 12.5, 15, months)

1. Interval H&P, weight
2. Fasting glucose, AST, ALT, GGT, albumin, alkaline phosphatase, total bilirubin, direct bilirubin, PT/INR, IGF-1
3. At 3, 6, 9, and 15 months, HbA1c
4. At 6 month visit only: ^1H -MRS/MRI of abdomen for quantification of liver fat and VAT, fibroscan, lipid panel

12 Month Visit

Identical to baseline visit except: ^1H -MRS/MRI of abdomen for quantification of liver fat and VAT will be performed; CCTA will not be performed. At the conclusion of the 12 Month Visit, subjects will self-administer

their first open-label injection, after which they will be observed for 30 minutes to ensure no allergic reaction.

18 Month Visit

1. Interval history, H&P
2. Fasting labs: glucose, IGF-I, AST, ALT, GGT, alkaline phosphatase, total bilirubin, lipid panel, HbA1c
3. Height, weight, anthropometrics
4. Whole body DXA scan for regional fat

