Liver Biopsy: Percutaneous liver biopsy will be performed under ultrasound guidance using a 16-gauge needle by experienced interventional radiologists. Participants with any contraindication to liver biopsy, including platelets < 75,000, elevated PT or PTT, or chronic anticoagulation use will not undergo biopsy. Individuals on aspirin for primary prevention of CVD may undergo biopsy following discontinuation of aspirin for ≥5 days. One biopsy fragment will be fixed in 10% formalin for histopathological analysis. Histologic scoring will use validated scoring systems NASH Clinical Research Network scoring system (93) and Brunt Fibrosis staging. NASH will be defined by the presence of: steatosis ≥1, lobular inflammation ≥1 and hepatocyte ballooning ≥1. Steatosis will be defined the presence of steatosis grade ≥1, not meeting criteria for NASH.

Fibrosis stage will be scored from 0-4 following the Brunt staging system. A second fragment will be placed in an RNA stabilization reagent (RNAlater, Qiagen) for gene expression analysis. Following RNA extraction, tissue RNA will be subjected to Counter digital transcript counting (Nanostring) analysis in [name] laboratory using customized codesets and probes specifically designed for key inflammation, fibrosis, and metabolism-related genes. This technique has been used successfully by his group to perform expression analysis of specific gene sets in peripheral blood and liver tissue from large numbers of patients.

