The total volume of blood sampling during the 18 months of the study is approximately 700cc. The maximum amount of blood drawn during any single visit will be 155cc, drawn at the baseline and 12 month visits. This amount of blood drawing is well within with our Human Research Committee guidelines, which urge precaution for blood sampling of more than 200cc on any given occasion and prohibit blood sampling of more than 550 cc in an 8-week period. There will be a minimum amount of discomfort associated with blood drawing and IV placement, with risks including minor bruising or bleeding or, much more rarely, infection, lightheadedness, or syncope.

Ionizing Radiation

Subjects will have 3 total body DXA scans (0, 12, and 18 months, 0.5 μ Sv each) and 1 coronary CT, with a median of 6mSv, with modest variation in dose for each individual since each exam is tailored to subject size, heart rate, and heart rhythm. The 95th percentile range for the cohort is estimated to be 2.0 – 12.7 mSv for the CCTA. Because subjects with BMI \geq 40kg/m² will not undergo CCTA, this will limit the upper level of radiation received by subjects from the CCTA. Thus, the total median radiation for the study will be 6.002mSv. For comparison, the average person in the United States receives a radiation exposure of 3.1mSv each year from natural background sources; thus the total radiation in the study will be equivalent to a little less than 2 years of natural background radiation. Scientists disagree regarding whether radiation at these low levels are harmful. In order to ensure that exposure to radiation from the study does not compound concurrent radiation exposure, we will exclude patients who report (1) any history of radiation therapy, (2) any significant radiation exposure over the course of the year prior to randomization, or (3) being under active consideration for a procedure or treatment that includes significant radiation exposure in the year following randomization. Please see the Research Strategy for more details.

Magnetic Resonance Imaging/Magnetic Resonance Spectroscopy

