Appendix 1: Summary of Procedures

| | Scr | BL | 2wk | 1m | 2m | 3m | 6m | 9m | 12m | 12.5m | 15m | 18m | ETV |
|---|-----|----|------------------|----|----|----|----|----|-----|-------|-----|-----|-----|
| Informed Consent | X | | | | | | | | | | | | |
| H&P | X | X | X | X | X | X | X | X | X | X | X | X | X |
| Weight | X | X | X | X | X | X | X | X | X | X | X | X | X |
| Height | X | | | | | | | | | | | | |
| Liver panel* | X | X | X (no GGT) | X | X | X | X | X | X | X | X | X | X |
| CBC | X | X | | | | | | | X | | | | |
| Creatinine | X | | | | | | | | | | | | |
| Fasting glucose | X | X | X | X | X | X | X | X | X | X | X | X | X |
| HbA1c | X | X | | | | X | X | X | X | | X | X | X |
| Hepatitis B sAg | X | | | | | | | | | | | | |
| Hepatitis C Ab | X | | | | | | | | | | | | |
| PSA (M only) | X | | | | | | | | | | | | |
| IGF-1 | | X | X | X | X | X | X | X | X | X | X | X | X |
| Lipid panel | | X | | | | | X | | X | | | X | X |
| Adiponectin | | X | | | | | | | X | | | | |
| IL-6 | | X | | | | | | | X | | | | |
| CRP | | X | | | | | | | X | | | | |
| CK18 | | X | | | | | | | X | | | | |
| 1H-MRS | X | | | | | | X | | X | | | X | X |
| 24h Food Recall | X | | | | | | | | X | | | X | X |
| Modifiable Activity Questionnaire | | X | | | | | | | X | | | X | X |
| Fibroscan | | X | | | | | X | | X | | | X | X |
| DXA scan | | X | | | | | | | X | | | X | X |
| Liver Biopsy | | X | | | | | | | X | | | | |
| Stable Isotopes – de novo lipogenesis | | X | | | | | | | X | | | | |
| CCTA** | | X | | | | | | | | | | | |
| PBMCs | | X | | | | | | | | | | | |

*Liver panel includes AST, ALT, GGT, albumin, total bilirubin, direct bilirubin, PT/INR, alkaline phosphatase.

**CCTA will be done only in individuals who meet the criteria described in the protocol

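### Elevated PTT bars liver biopsy, but PTT is scheduled only at screening, so the newest scheduled value is over 12 months old at the month-12 biopsy

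*Combined protocol and SAP*

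**What the plan says.** The biopsy rule is in IV. Study Procedures, Methods, Liver Biopsy, and is repeated in VI. Risks and Discomforts, Liver biopsy. Among other contraindications, participants with "elevated PT or PTT, or chronic anticoagulation use will not undergo biopsy". Neither place limits the rule to screening or states how recent the result must be. Biopsies are planned at baseline and at month 12.

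The laboratory lists in IV. Study Procedures are:

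- Screen Visit, item 3: "alkaline phosphatase, PT/INR and PTT, CBC, glucose, HbA1c".
- Baseline Visit, item 2: "alkaline phosphatase, albumin, lipid panel, CBC, PT/INR, HbA1c, frozen serum for adiponectin".
- Safety Visits, item 2: "alkaline phosphatase, total bilirubin, direct bilirubin, PT/INR, IGF-1".
- 12 Month Visit: "Identical to baseline visit except" that MRS/MRI is added and CCTA is dropped.

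Appendix 1 has no PTT row. Its footnote reads "Liver panel includes AST, ALT, GGT, albumin, total bilirubin, direct bilirubin, PT/INR, alkaline phosphatase".

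Baseline Visit, item 7 adds a condition: "Biopsy will not be done if performed in the 12 months prior to baseline", provided that no new treatment was started and weight has not changed by more than 10% since then.

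**The concern.** The protocol names three laboratory contraindications to biopsy: low platelets, elevated PT and elevated PTT. At month 12 the CBC and PT/INR are drawn again, so the first two can be judged on current values. PTT is not drawn again, so the third rests on the screening result.

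No eligibility criterion uses PTT. Its only stated use in the documents is the biopsy rule, and the schedule supplies it ahead of the first biopsy but not the second. Where a recent clinical biopsy replaces the baseline one, the month-12 biopsy is the first that the study itself performs.

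What is at stake is participant safety at a research procedure for which the protocol lists bleeding as a risk. The primary MRS endpoint, the power calculation and the alpha level are not affected.

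**Working it through.** The plan gives no figure to reproduce here. The check compares the lists and then works out the age of the PTT result.

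**1. Tests listed at each draw up to month 12** (Screen, Baseline, Safety and 12 Month Visit lists, compared with Appendix 1)

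| Draw | PT/INR | PTT | Study biopsy |
|---|---|---|---|
| Screening | yes | yes | no |
| Baseline | yes | no | yes, unless a recent biopsy is used |
| 0.5, 1, 2, 3, 6 and 9 months (6 draws) | yes | no | no |
| Month 12 | yes | no | yes |

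Number of draws = 1 + 1 + 6 + 1 = 9. PT/INR is listed at 9 of 9 and PTT at 1 of 9. The unscheduled repeat bloods in the liver-injury algorithm also use PT/INR without PTT.

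**2. Age of the newest scheduled PTT at the month-12 biopsy**

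Age = g + 12 months, where g is the interval from screening to baseline. Randomization takes place between the two visits (III. Subject Enrollment, Randomization), so g is greater than 0 and the nominal age exceeds 12 months. The protocol states neither a maximum for g nor a window for the month-12 visit. Taking g as 2 to 8 weeks, as an assumption:

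- g = 2 weeks = 0.46 month, so age = 12 + 0.46 = about 12.5 months.
- g = 8 weeks = 1.84 months, so age = 12 + 1.84 = about 13.8 months.

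An interval of 12 weeks (2.76 months) would give about 14.8 months. With PTT in the month-12 pre-biopsy bloods, the age falls to about 0.

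**3. What other safeguards cover**

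- PT/INR is current at month 12.
- Medication changes are recorded at each visit, which should bring a new anticoagulant to light (Concomitant Medications).
- Cirrhosis or decompensation leads to discontinuation (Study Drug).
- The INR criterion in part B of the liver-injury algorithm stops study drug permanently. After that the protocol plans no further research follow-up, so a month-12 research biopsy would not be expected.

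None of these measures PTT. What they leave uncovered is a new PTT elevation with normal PT/INR in someone not taking an anticoagulant. The documents give no rate for this, so no number of affected participants can be stated.

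**4. Room in the blood volume**

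VI. Risks and Discomforts, Blood drawing states: "The maximum amount of blood drawn during any single visit will be 155cc, drawn at the baseline and 12 month visits". The institutional precaution level is 200cc, so the margin is 200 - 155 = 45cc.

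**The case against.** The strongest reply is that the schedule is not the whole of practice. The biopsies are done by experienced interventional radiologists under a rule that forbids biopsy when PTT is elevated. That rule can be read as already requiring a known PTT, so all that is missing is a line in a laboratory list. The rule also sets no look-back window, so calling a value of more than 12 months too old draws on clinical convention, not on a limit in the protocol. Appendix 1 is weak support, because it omits PTT even at screening, where the text requires it. Finally, the residual risk is small and no rate is given.

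Much of this stands, and it is why the point is minor. The documents cannot show that any biopsy would go ahead on an old PTT. They also do not describe a pre-procedure coagulation test: standard radiology procedure is mentioned only for observation after the biopsy. Appendix 1 may be set aside, since the visit lists alone establish the gap. A current PT/INR does not answer the PTT part of the rule, because the protocol names the two tests separately.

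A second objection is that the added test could cost data. A cancelled month-12 biopsy removes that participant's follow-up histology and liver gene expression (Aims 1b, 2b and 2c). That is true, but the existing rule already forbids any such biopsy. The test would enforce the rule and would not add a restriction.

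**Conclusion.** The concern holds, as a minor correction for participant safety. On the protocol's own schedule, one of its three laboratory contraindications to biopsy has no current value at month 12: PTT is listed at 1 of 9 draws and PT/INR at 9 of 9. That the newest scheduled PTT is nominally more than 12 months old follows from the order of visits alone. The range of 12.5 to 13.8 months rests on the assumed interval of 2 to 8 weeks.

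The conclusion concerns scheduled tests only and would lose its practical force if interventional radiology routinely checks PTT before biopsy. It does not extend to platelets or PT/INR, both of which are drawn again at month 12.

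**What to change.** Add PTT to the 12 Month Visit fasting bloods, drawn with the CBC and PT/INR already listed and before the biopsy day. Add a PTT row to Appendix 1, marked at screening and month 12.

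The cost is one assay on an existing draw, well inside the 45cc margin. There is one sequencing requirement: the blood must be taken before the biopsy. This is feasible, because the month-12 assessment may be spread over 2 to 3 days and the protocol expects the biopsy usually to fall on a different day from the other procedures.

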intake are contributing to the observed treatment effect on hepatic fat, histologic and metabolic variables. If so, we will include these variables in the analyses and modeling as adjusted covariates. If any other variables are different between groups, such as medication adherence, these will also be included as covariates.

Genetic analyses: Hepatic mRNA expression for the targeted genes listed above will be quantified at baseline and 12 months. Our statistician, [name], has designed a stepwise analysis that will serve as an appropriate approach for this sample size and the discrete set of genes that we propose to measure. (1) We will first assess whether there are significant changes in expression between baseline and 12 months in the GHRH-treated subjects, using paired samples t-test. (2) For genes that show a significant change in expression in this analysis, we will then compare fold-changes in expression between the tesamorelin and placebo groups. False discovery rate based type-1 error adjustment will be applied for multiple comparisons. (3) Genes with differential changes in the tesamorelin vs. placebo groups will be further investigated by assessing associations between mRNA expression and histological and biochemical parameters. For example, if SREBP1c is found to be downregulated in tesamorelin compared to placebo groups, we will assess correlations between mRNA expression of SREBP1c and histological steatosis score as well as rate of *de novo* lipogenesis quantified using stable isotopes.

Missing data: We expect that the pattern of any missing data will be at random (MAR), and the longitudinal mixed effects model approach utilizing all available observation will provide unbiased effect size estimates. However, we will perform sensitivity analyses if the dropout rate is higher than expected or differs between groups. We will initially consider applying the last observation carried forward (LOCF) as a conservative approach. We will also consider multiple imputations (MI) based analysis.

Open label analysis: For the 6-month open-label extension, hepatic fat and relevant secondary endpoints including fibrosis as assessed by Fibroscan, and AST and ALT will be determined. We will first examine the 18 month effects by comparing 0-18 months mean change of Group 1 (initially randomized to tesamorelin and maintaining active treatment from month 12-18) to that of Group 2 (initially randomized to placebo and crossed over to tesamorelin from months 12-18) using independent samples t-test, and then compare mean change over 1 year to that over the later 6 months within Group 1 using paired samples t-test. Although the primary purpose of the 6-month open label extension is to increase recruitment and retention, analysis of data from the group receiving tesamorelin for 18 months will provide information regarding whether reductions in liver fat translate into sustained longer-term improvements in transaminases and liver fibrosis as measured by FibroScan and will provide longer-term safety data in this group.

Sample Size and Power Calculations

Aim 1a (Primary endpoint): In our previous study of tesamorelin in HIV (see Preliminary Data), the change in liver fat over 6 months among individuals who started with hepatic fat fraction >5% was -2.5 ± 11.9 lipid-to-water percent in placebo vs. -9.1 ± 7.6 lipid-to-water percent in tesamorelin. Based on the prior data, we assumed that the pooled standard deviation of the 1 year change is 8% and the tesamorelin treatment effect over 1 year (difference in tesamorelin vs. placebo changes) is at least a 7 point change in the lipid to water percentage. Using this data we estimate that an initial sample size of 76 will provide 91% power to detect a clinically relevant treatment difference of 7% or larger 1 year mean changes in liver fat (lipid to water %) at $\alpha = 0.05$ if the discontinuation rate is 20% (61 evaluable patients), or 80% power if the discontinuation rate is 25%. In the prior study of tesamorelin led by [name], discontinuation rate was 14% after 6 months (69). These assumptions are conservative as we expect that the 1 year mean change in the current proposed trial among the patients on tesamorelin will be greater than that was observed above in our 6 month preliminary studies. We also anticipate the variability over time will be less in the placebo group assessed by repeated measures in the proposed study rather than a single point in time as in our prior study. **Aim 1b:** Based on baseline data from PIVENS (25), in which the standard deviation in NAS is 1.4, we will have >90% power to detect a change of 2 in NAS. **Aims 2-3:** For analysis of the variables in Aims 2-3, it is important to note that the purpose of the study is to interrogate physiology, and the sample size is relatively limited due to the detailed assessments performed. Thus, these variables will be largely viewed as hypothesis generating, and statistical analyses will be interpreted in such a context. (For example, if there is a marginally significant change in one lipogenic gene but no signal in other genes, this will not be considered meaningful, whereas a trend toward change in all

lipogenic genes in the same direction may be meaningful). Thus we do not plan to correct Type 1 error for multiple comparisons, which would limit power and increase the probability of Type 2 error (99, 100). For the variables in Aims 2-3, the sample size will provide 80% power to determine a 0.73 SD difference in 1 year mean changes between treatment groups at $\alpha = 0.05$ with 61 evaluable patients. Although changes of <0.7 SD in some of these variables may be clinically relevant, most clinically meaningful effects are expected to be 1SD or more, a magnitude for which the study is sufficiently powered.

VI. Risks and Discomforts

GHRH (Tesamorelin)

In previous large, placebo-controlled studies of tesamorelin in HIV-infected individuals, adverse events that were more common in the treatment vs. placebo group were injection site erythema (8.5% in treated vs. 2.7% in placebo), injection site pruritis (7.6% of treated vs. 0.8% placebo), and peripheral edema (6.1% in treated vs. 2.3% in placebo). With respect to serious adverse events (SAEs), prevalence was not statistically different (3.7% in treated vs. 4.2% in placebo). There is a risk of hyperglycemia with GHRH, particularly in the few weeks following initiation of treatment, but glycemia returns to baseline after several months. Clinically significant changes have not been observed for liver function (alanine aminotransferase or aspartate aminotransferase), kidney function (creatinine), or blood pressure (diastolic and systolic).

With regard to injection site reactions, subjects will be informed to notify a study investigator of any sign of erythema, swelling, or pruritis, and subjects with erythema and/or pruritis extending beyond the immediate injection site will be discontinued from the study. Subjects will also be informed of risks associated with excess GH, including arthralgia, paresthesia, and hyperglycemia. Although there is a theoretical risk of neoplasm with an agent that increases GH and IGF-I, there is no evidence of increased malignancy with tesamorelin. This risk is further minimized based on the data from previous studies showing achievement of physiologic, rather than pharmacologic, increases in IGF-1 SD scores. Nonetheless, subjects with active malignancy will be excluded from the study. Further, men with history of prostate cancer or PSA >5 ng/mL, or women 50 years or older without documentation of negative mammogram in the past year will be excluded from the study. To minimize the risk of hyperglycemia, subjects with known diabetes or with fasting glucose >126 mg/dL or HbA1c $\geq 6.5\%$ will be excluded from the study.

Liver biopsy

Ultrasound-guided percutaneous liver biopsy will be performed by trained interventional radiologists who specialize in gastrointestinal procedures at the MGH. Subjects will be observed as outpatients following liver biopsy per standard interventional radiology procedure. The risks associated with liver biopsy include pain, transient hypotension (vasovagal response), bleeding, and transient bacteremia. Participants with any contraindication to liver biopsy, including platelets $< 75,000$, elevated PT or PTT, or chronic anticoagulation use will not undergo biopsy. Individuals on aspirin for primary prevention of MI may undergo biopsy following discontinuation of aspirin for ≥ 5 days. After discharge from interventional radiology following the procedure and outpatient observation, subjects will also be called the next day by study staff to ensure that any post-procedure pain has resolved and that no new symptoms are present. Subjects with persistent pain or other concerning symptoms will be asked to return for evaluation. Drs. [name] and [name] have successfully conducted previous studies with liver biopsies performed as described above.

Blood drawing

The total volume of blood sampling during the 18 months of the study is approximately 700cc. The maximum amount of blood drawn during any single visit will be 155cc, drawn at the baseline and 12 month visits. This amount of blood drawing is well within with our Human Research Committee guidelines, which urge precaution for blood sampling of more than 200cc on any given occasion and prohibit blood sampling of more than 550 cc in an 8-week period. There will be a minimum amount of discomfort associated with blood drawing and IV placement, with risks including minor bruising or bleeding or, much more rarely, infection, lightheadedness, or syncope.

Ionizing Radiation

Subjects will have 3 total body DXA scans (0, 12, and 18 months, 0.5 μ Sv each) and 1 coronary CT, with a median of 6mSv, with modest variation in dose for each individual since each exam is tailored to subject size, heart rate, and heart rhythm. The 95th percentile range for the cohort is estimated to be 2.0 – 12.7 mSv for the CCTA. Because subjects with BMI \geq 40kg/m² will not undergo CCTA, this will limit the upper level of radiation received by subjects from the CCTA. Thus, the total median radiation for the study will be 6.002mSv. For comparison, the average person in the United States receives a radiation exposure of 3.1mSv each year from natural background sources; thus the total radiation in the study will be equivalent to a little less than 2 years of natural background radiation. Scientists disagree regarding whether radiation at these low levels are harmful. In order to ensure that exposure to radiation from the study does not compound concurrent radiation exposure, we will exclude patients who report (1) any history of radiation therapy, (2) any significant radiation exposure over the course of the year prior to randomization, or (3) being under active consideration for a procedure or treatment that includes significant radiation exposure in the year following randomization. Please see the Research Strategy for more details.

Magnetic Resonance Imaging/Magnetic Resonance Spectroscopy

Subjects will be carefully screened for metal implants such as surgical clips or pacemakers prior to MRI scanning. Subjects will be given earplugs due to the loud noises during the test. Subjects who feel uncomfortable in confined spaces may have difficulty in the narrow cylinder of the MRI, and the MRI can be stopped at any time at the patient's request. A low dose of lorazepam may be administered at the time of MRI/MRS for patients who have a history of claustrophobia. Lorazepam is a benzodiazepine used to treat anxiety. It may cause drowsiness, dizziness, or unsteadiness. Patients will be cautioned to not combine this medication with other sedating medications or alcohol. We will also ensure that the patient is driven home by someone else.

Contrast-enhanced Coronary Computed Tomography Angiography (CCTA)

CCTA will involve the use of contrast as well as nitroglycerin, with risks as below.

CT Contrast Medium

Coronary CT angiography requires the injection of an iodinated contrast medium. These contrast media have been known to cause renal failure, particularly in patients with a pre-existing renal impairment. An eGFR will be reviewed for all participants prior to their undergoing contrast administration. Subjects with GFR < 60 will be excluded. Participants on metformin will be asked to hold metformin 48 hours prior to CT scan as well as 48 hours after the scan. We will check with the participant's physician to ensure this is safe; if the physician feels that holding metformin is not safe, the participant may participate in the study but will not have the CT scan. Adequate hydration will also be emphasized to each study participant. The contrast dose in cardiac CT has decreased with the introduction of faster scanners. The dose required will be between 75 to 100 ml. Allergic reactions to iodinated contrast media may cause skin reactions or in very rare occasions result in breathing difficulty and hypotension. Subjects will be closely monitored for the development of any allergic reactions.

Nitroglycerin:

Nitroglycerin is commonly used in patients with angina pectoris and is generally considered safe. The side-effects and risks of nitroglycerin are generally mild and of short duration and include hypotension, tachyarrhythmia, headache, lightheadedness, and visual disturbance. Subjects who are on sildenafil, tadalafil, or vardenafil will need to stop these drugs at least 3 days prior to receiving nitroglycerin on the day of the cardiac CT scan. Nitroglycerin will not be administered to subjects who have taken sildenafil, tadalafil, or vardenafil within 3 days of the cardiac CT scan. If baseline systolic blood pressure is below 90, nitroglycerin will not be given. If a participant's blood pressure were to drop precipitously or if the participant develops symptoms, standard clinical care will be provided.

Stable Isotope Test

Drinking deuterated water may cause transient dizziness, nausea, or – less commonly – vomiting. Literature suggests that this occurs with ingestion of larger amounts of 100-200cc at one time (Miller et al., J Appl Physiol

128: 1163–1176, 2020). Because of this, we will offer those with weight $\geq 100\text{kg}$ the option to forego the test if they are worried about the risk of these transient side effects.

Incidental Findings

Non-cardiac incidental findings may be discovered on the MRI of the liver and abdomen or on the CCTA. Additionally, clinically actionable cardiac findings will be reported from the CCTA in real-time. These findings will be communicated to the subject and, with the subject's permission, his/her regular care providers. When necessary, we will help facilitate follow-up for findings that require timely evaluation or treatment. Incidental findings may cause worry and additional diagnostic clinical procedures for subjects. Of note, non-actionable cardiac findings on the CCTA will not be reported to subjects, who will be informed in the consent process that the scan is for research, is not meant to replace their routine care or provide cardiovascular screening, and will not be available to them. As above, findings such as severe stenosis of a vessel that are clinically actionable will be reported and communicated to subjects.

Fibroscan and Liver Ultrasound do not have direct risks, although either may cause discomfort from lying supine, temporary soreness at the site of the scan, or a skin reaction to the ultrasound gel used.

VII. Potential Benefits

Potential Benefits of the Proposed Research to Human Subjects and Others

All participants will receive nutrition counseling from Registered Dietitians, and will receive information about their metabolic and nutritional health. Our preliminary data suggest that the study drug results in a reduction in visceral fat in a majority of patients and, on average, reduces systemic inflammation, triglyceride levels, and carotid intima-medial thickness; these are potential benefits for subjects randomized to study drug during the double-blind phase and for all subjects in the open-label phase. The moderate level of risk involved in study participation is thus thought to be balanced by the possible benefits to participants. This study investigates a novel therapy for NAFLD and, if the study hypotheses are correct, has the potential to lead to a treatment for NAFLD that would be of benefit to the larger population.

Importance of the Knowledge to be Gained

NAFLD is a prevalent disease that poses significant health consequences. Further, there is currently a lack of effective pharmacological therapies, and the development of strategies for treatment is urgent. The current proposal will investigate a novel strategy to address underlying pathophysiology of NAFLD, and may result in significant progress toward development of a therapy. Even if the hypotheses are proven incorrect, the proposed research will provide data that allow for significant insight into the pathophysiology of NAFLD as well as the metabolic and endocrine processes related to NAFLD. Thus the potential benefits to the study population outweigh the risks of participation.

XI. Monitoring and Quality Assurance

Data Quality and Monitoring

Data will be collected on written Case Report Forms that are maintained in each subject's binder along with source documentation. Data will be entered into REDCap; double-data-entry will be used to ensure correctness of data.

The study investigators will monitor all data collected for the studies, and will ensure completeness and timeliness of data collection and entry. Data will be stored securely, with access restricted to co-investigators and study staff. Binders with subject information will be labeled with coded enrollment number to protect confidentiality. Electronic databases will be locked, and password-protected, with access available only to study staff. Data will not be saved on the hard drive of any laptop or desktop computers or on any removable data storage devices such as flash drives or CDs.

Safety Monitoring

The Co-PIs of the study will monitor adverse events in real time. There are individual stopping rules as above. There are no study stopping rules, but the study will have ongoing monitoring by a Data Safety Monitoring Board (DSMB).

A DSMB will be established by the Co-PIs and that will consist of a statistician as well as 2 physicians with expertise in endocrinology and hepatology. The DSMB will meet every 6 months by telephone or in person to review all adverse events as well as recruitment and retention information, protocol deviations, and any unanticipated problems.

Adverse Events

An adverse event is any untoward or unfavorable medical occurrence in a human subject, including any abnormal sign (e.g., abnormal physical exam or laboratory finding), significant symptom, or disease, temporally associated with the subject's participation in the research, whether or not considered related to the research.

Adverse events will be judged by the Co-PIs or Co-Investigators based on seriousness, causality, and expectedness. Adverse events will be graded using the National Cancer Institute Common Terminology Criteria for Adverse Events (CTCAE) Version 5.0 grading system

(https://ctep.cancer.gov/protocoldevelopment/electronic_applications/ctc.htm#ctc_50)

A **serious adverse event** is one that results in one or more of the following:

- death
- a life threatening (i.e., an immediate threat to life) event
- an inpatient hospitalization or prolongation of an existing hospitalization
- a persistent or significant incapacity or substantial disruption of the ability to conduct normal life functions
- a congenital anomaly/birth defect
- a medically important event*

* Medical and scientific judgment will be exercised in deciding whether expedited reporting is appropriate in other situations, such as important medical events that may not be immediately life threatening or result in death or hospitalization but that may jeopardize the subject or may require intervention to prevent one of the other outcomes listed above.

Causality will be defined as follows and will be judged by a Co-PI or Co-Investigator:

Definitely Related

- reasonable temporal relationship
- follows a known response pattern
- clear evidence to suggest a causal relationship
- there is no alternative etiology

Probably Related

- reasonable temporal relationship
- follows a suspected response pattern (based on similar agents)
- no evidence of a more likely alternative etiology

Possibly Related

- reasonable temporal relationship
- little evidence for a more likely alternative etiology

Unlikely Related

- does not have a reasonable temporal relationship
OR
- good evidence for a more likely alternative etiology

Not Related

- does not have a temporal relationship
OR
- definitely due to an alternative etiology

Note: Other factors (e.g., dechallenge, rechallenge) should also be considered for each causality category when appropriate. Causality assessment is based on available information at the time of the assessment of the AE. The investigator may revise the causality assessment as additional information becomes available.

Expectedness will be determined based on the information in the investigator's brochure (IB) or package insert (PI), as well as the known side effects of growth hormone excess, and the known risks of study procedures. Adverse events that are not listed in the IB or PI, and are not known side effects of GH excess or possible side effects of study procedures will be judged as unexpected. The determination of expectedness will be made by a Co-PI or Co-Investigator.

AEs will be reported to the Partners IRB per IRB guidelines. Serious adverse events that are unexpected and thought to be related to the study will be reported to the IRB per IRB guidelines and to the FDA per FDA guidelines.

Subjects will be instructed to report immediately any adverse events. A physician or nurse practitioner will be available on-call 24 hours/day, 7 days/week, to all study participants for any questions or concerns.

X. References

